### **7.5.4 ICU LOS and ICU mortality**

ICU length of stay and mortality will be considered in Cohort 1 and among subjects in Cohort 2 who are admitted to an ICU. ICU mortality will be estimated as the observed proportion of subjects who died during the hospital stay and presented with a 95% exact Clopper-Pearson confidence interval. ICU length of stay will be considered only among subjects discharged alive and will be summarized with median and inter-quartile range.

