**Summary of Outcome measures:**

- Transfer to ICU for hospitalized non-ICU patients
- Increased O2 requirement (PaO2/FiO2 ratio or SpO2/FiO2), supplemental oxygen strategy (nasal cannula, high flow nasal cannula, noninvasive ventilation, intubation and invasive mechanical ventilation, rescue ventilation i.e. neuromuscular blocking agents, prone positioning, corticosteroids, ECMO)
- Use of vasopressors, ventilated days, renal support
- ICU LOS, ICU mortality
- Hospital LOS, Hospital mortality
- 28-day mortality

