**Secondary endpoints:**

1. Type and duration of respiratory support
2. Overall Mortality within first 60 days
3. Hospital LOS and in hospital mortality
4. ICU LOS and ICU mortality
5. Ventilator-free days (non-ICU cohort)
6. Incidence of secondary infections / co infections

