##### **Secondary endpoints:**

1. Type and duration of respiratory support (see definitions in Section 7.5.1)
2. Overall Mortality within first 60 days
3. Hospital LOS and in hospital mortality
4. ICU LOS and ICU mortality
5. Ventilator-free days (non-ICU cohort)
6. Incidence of secondary infections / co infections

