### **5. Study population**

Patients will be enrolled in 2 cohorts independent of each other. Cohort 1 will consist of patients who are admitted to the ICU. Cohort 2 will consist of patients who are admitted to a non-ICU floor. Patients transferring from non-ICU to ICU floors or vice versa will be

analyzed in the cohort corresponding to the location of signing consent. Each cohort will be analyzed independently.

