## 7. Statistical considerations

Patients will be enrolled in 2 cohorts independent of each other. Cohort 1 will consist of 41 patients who are admitted to the ICU. Cohort 2 will consist of 90 patients who are admitted to a non-ICU floor. The two cohorts will be analyzed independently. For sample size considerations please see section 7.6.

For each cohort, descriptive summaries of continuous and other numeric variables will consist of the summary statistics: median, minimum and maximum values. Categorical variables will be summarized by the frequency and proportion of subjects falling into each category. Unless otherwise indicated, percentages in tables will be column percentages, using the total number of observations in the population as the denominator. Exact confidence intervals for binomial proportions will be derived using the Clopper-Pearson method.

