### **7.5.3 Hospital LOS and in-hospital mortality**

In-hospital mortality will be estimated as the observed proportion of subjects who died during the hospital stay and presented with a 95% exact Pearson confidence interval. Hospital length of stay will be considered only among subjects discharged alive and will be summarized with median and inter-quartile range.

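### Section 7.5.4 counts any hospital death as ICU mortality, so in Cohort 1 the endpoint repeats in-hospital mortality and no estimate of death in the ICU is defined

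*Combined protocol and SAP*

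**What the plan says.** The Secondary endpoints lists, in the protocol summary and again in Section 4.1, give "Hospital LOS and in hospital mortality" as item 3 and "ICU LOS and ICU mortality" as item 4. The Summary of Outcome measures likewise has "ICU LOS, ICU mortality" on one line and the hospital outcomes on the next.

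The analysis section then defines both mortality estimates:

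- Section 7.5.3: "In-hospital mortality will be estimated as the observed proportion of subjects who died during the hospital stay".
- Section 7.5.4: "ICU mortality will be estimated as the observed proportion of subjects who died during the hospital stay".

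Section 7.5.4 fixes the population first: "ICU length of stay and mortality will be considered in Cohort 1 and among subjects in Cohort 2 who are admitted to an ICU".

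Two further statements matter. Section 7 says that "Cohort 1 will consist of 41 patients who are admitted to the ICU". Section 5 says that subjects who move between ICU and floor are "analyzed in the cohort corresponding to the location of signing consent. Each cohort will be analyzed independently". No other part of the documents limits ICU mortality to deaths that occur in the ICU.

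**The concern.** ICU mortality is ordinarily read as death in the ICU. The rule in 7.5.4 counts death anywhere in the hospital. A subject who leaves the ICU and later dies on a ward is counted as an ICU death, and in Cohort 1 the endpoint cannot differ from the one before it.

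At stake is the mortality half of secondary endpoint 4. In Cohort 1 it adds nothing to endpoint 3, and in neither cohort does the plan define an estimate of death in the ICU. An analyst who follows the text reports hospital deaths under an ICU label. One who counts ICU deaths instead departs from the written plan, and in an open-label study may do so with outcomes already known. ICU length of stay remains informative.

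**Working it through.** The plan states no mortality figure, so there is none to reproduce. The check compares the two definitions and then sizes the difference.

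**1. The definitions side by side**

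| | In-hospital mortality (7.5.3) | ICU mortality (7.5.4) |
|---|---|---|
| Event | death in the hospital stay | death in the hospital stay |
| Denominator, Cohort 1 | all of Cohort 1 | all of Cohort 1 |
| Denominator, Cohort 2 | all of Cohort 2 | those admitted to an ICU |
| Interval | exact 95% | exact 95% |

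Section 7.5.3 calls its interval exact Pearson and 7.5.4 calls its interval exact Clopper-Pearson. This makes no difference, because Section 7 sets Clopper-Pearson for all exact binomial intervals.

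**2. Cohort 1 (n = 41, Section 7)**

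Let D be the hospital deaths, of which w follow ICU discharge.

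- In-hospital mortality: D/41.
- ICU mortality as written: D/41, for any w.
- ICU mortality if only deaths in the ICU count: (D − w)/41.
- Difference: w/41, which is 1/41 = 2.4 points for each such death and 0 if w = 0.

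The documents give neither D nor w, so the values below are assumptions. For x deaths among n subjects, the Clopper-Pearson limits are the 2.5% quantile of Beta(x, n − x + 1) and the 97.5% quantile of Beta(x + 1, n − x).

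| D | w | As written, both endpoints | Deaths in the ICU only |
|---|---|---|---|
| 11 | 1 | 11/41 = 26.8% (14.2–42.9) | 10/41 = 24.4% (12.4–40.3) |
| 12 | 0 | 12/41 = 29.3% (16.1–45.5) | 12/41 = 29.3% (16.1–45.5) |
| 12 | 2 | 12/41 = 29.3% (16.1–45.5) | 10/41 = 24.4% (12.4–40.3) |
| 12 | 4 | 12/41 = 29.3% (16.1–45.5) | 8/41 = 19.5% (8.8–34.9) |

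**3. Cohort 2 (n = 90, Section 7)**

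Let m be the number admitted to an ICU. It is not given and cannot exceed 90. The two estimates can differ here. If m = 30, with 9 deaths among those subjects and 3 among subjects never in an ICU, in-hospital mortality is 12/90 = 13.3% and ICU mortality as written is 9/30 = 30.0%. Those 9 may still include ward deaths after ICU discharge.

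If death in the ICU is meant, each such ward death adds 1/m:

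- m = 20: 5.0 points.
- m = 40: 2.5 points. With 8 ICU deaths assumed, one ward death moves 8/40 = 20.0% (9.1–35.6) to 9/40 = 22.5% (10.8–38.5).
- m = 90, the logical limit: 1.1 points.

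The planning rates narrow this a little. ICU transfer is one component of the Cohort 2 composite, which Sections 7.3 and 7.6 put at 60% under the null and 45% at the target. Expected transfers are then at most 0.60 × 90 = 54 or 0.45 × 90 = 40.5. At those ceilings one ward death adds 1/54 = 1.9 or 1/40.5 = 2.5 points; with fewer transfers it adds more.

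**The case against.** The strongest reply is that 7.5.4 opens by fixing a population of ICU-admitted subjects, so ICU mortality may simply mean the hospital mortality of ICU patients. The definition is explicit, it yields a distinct figure in Cohort 2, and a report that prints it misleads nobody. On this view the remedy is a matter of terminology. The endpoint is also descriptive, with no test or threshold. Every death in the hospital stay is still counted in 7.5.3, and 60-day mortality is estimated in 7.5.2. The sizes rest on assumed counts: a shift of 2.4 points sits inside an interval 40.3 − 12.4 = 27.9 points wide, and it may be zero.

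Much of this stands. The effect is small, confined to one descriptive endpoint, and depends on deaths that may not occur. The population reading is possible, and the text does not exclude it.

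It does not remove the problem. Under that reading the Cohort 1 estimate is an exact copy of 7.5.3, although the plan lists two endpoints, and the label still suggests something else. Under the other reading the wrong event is counted. Either way 7.5.4 needs an edit.

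**Conclusion.** The concern holds. That the two Cohort 1 mortality estimates coincide follows from the definitions and needs no assumption about the data. The label mismatch applies to both cohorts.

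Overstatement is conditional. It arises only if death in the ICU was intended and at least one subject dies in hospital after leaving the ICU. The direction is claimed for the index hospitalization only, since 7.5.2 recognises discharge to another hospital, where a later ICU death could occur. All death counts and values of m used above are illustrations, not expected errors.

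The definition should be corrected. It does not affect the primary hypotheses, the sample sizes or the 60-day Kaplan-Meier estimate.

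**What to change.** State which quantity is meant and name it accordingly.

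- **If death in the ICU:** change the event in 7.5.4 to *death during an ICU stay in the index hospitalization, including any ICU readmission*, and leave 7.5.3 to cover all hospital deaths. Restricting to the index hospitalization and counting readmissions are choices the plan does not now make, so the sponsor should confirm them.
- **If hospital death:** rename the estimate *in-hospital mortality among ICU-admitted subjects*, report it for Cohort 2, and drop it for Cohort 1 as a repeat of 7.5.3.

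In the same edit, say whether the restriction of ICU length of stay to survivors refers to discharge from the ICU or from the hospital.

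The cost is one sentence, plus that clarification. No new data are needed: ICU admission and discharge dates and death dates are already required for ICU length of stay and mortality.

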### 7.5.5 Ventilator-free days

Ventilator-free days will be considered only in Cohort 1. It will be defined as the number of days during 28 days after the intervention that the subject is alive and does not require ventilator support. Ventilator-free days will be summarized with median and inter-quartile range.

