## **7.5 Analysis of secondary endpoints**

### **7.5.1 Type and duration of respiratory support**

The number of patients requiring each type of respiratory support will be tabulated. The duration of support will be summarized with median and inter-quartile range. For the purposes of this protocol respiratory support will be captured and classified in the following categories:

1. Supplemental Oxygen by nasal cannula, simple mask, non-rebreather mask and defined by flow rate in liters/min
2. High Flow Nasal Oxygen with flow rates and FiO2 setting
3. Non-invasive positive pressure ventilation with flow, FiO2 and pressure settings defined
4. Mechanical Ventilation with FiO2, Pressure and ventilator settings defined
5. Extra corporeal Membrane Oxygenation (ECMO).

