### **7.5.2 Overall mortality within first 60 days**

The overall survival of the subjects will be estimated using the Kaplan-Meier method and presented with 95% confidence bands. Subjects may be censored if they had a routine discharge (not hospice, or another hospital), and could not be contacted for further follow-up. Overall mortality at 60 days post-intervention will be estimated using the Kaplan-Meier estimate.

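### Ventilator-free days keep full credit for days before death, so a patient who dies can outrank a survivor who recovers from ventilation; duration of support has no rule for death

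*Combined protocol and SAP*

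**What the plan says.** Section 7.5.5 defines the score as "the number of days during 28 days after the intervention that the subject is alive and does not require ventilator support" and its reporting as follows: "Ventilator-free days will be summarized with median and inter-quartile range". It gives no test and no separate score for death.

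On the population, section 7.5.5 states: "Ventilator-free days will be considered only in Cohort 1". The secondary endpoint lists in the Protocol Summary and section 4.1 label the same measure for the other cohort: "Ventilator-free days (non-ICU cohort".

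Section 7.5.1 covers type and duration of respiratory support. Its rule for duration is: "The duration of support will be summarized with median and inter-quartile range". It names no analysis population and does not mention death.

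Sections 7.5.3 and 7.5.4 do address death for a similar quantity: hospital and ICU length of stay are summarised only in patients who leave alive. Mortality is reported separately. For example, section 7.5.2 says: "Overall mortality at 60 days post-intervention will be estimated using the Kaplan-Meier estimate". No section links mortality to the ventilator-free score.

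**The concern.** A score called ventilator-free days will usually be read as a scale on which more is better. On the written definition, the same mid-range value can mean a patient who recovered after some days of ventilation or a patient who died after some days without it. The median and IQR cannot tell these apart.

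This can happen in the planned population. Cohort 1 is defined by ICU location (section 5). Eligibility does not require ventilation; it only excludes ventilation lasting more than 14 days (section 5.1). The cohort can therefore contain patients never ventilated, patients on a ventilator and patients who come off one, and some may die while off it.

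Duration of support has a more direct form of the problem. Death on the ventilator ends the count, so it produces a short duration that looks the same as early recovery. The plan guards against this for length of stay but not here. The trial has no control arm in which the same distortion would appear, so readers would take the summaries at face value.

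**Working it through.** The plan states no figure for ventilator-free days, so there is nothing to reproduce. The check applies the written definition.

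**Inputs from the documents.** The window is "during 28 days after the intervention", so the maximum is 28. A day counts if the patient is alive and off the ventilator (section 7.5.5). The cohort size is given in section 7: "Cohort 1 will consist of 41 patients who are admitted to the ICU".

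**Step 1: individual scores.** Score = number of days from 1 to 28 that are both alive and off the ventilator. The day of death is counted here.

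| Course | Written rule | Death by Day 28 scored 0 |
|---|---|---|
| Never ventilated, dies on Day 20 | 20 | 0 |
| Ventilated Days 1–10, off, dies on Day 27 | 27 − 10 = 17 | 0 |
| Ventilated Days 1–5, off, dies on Day 20 | 20 − 5 = 15 | 0 |
| Ventilated 10 days, alive at Day 28 | 28 − 10 = 18 | 18 |
| Ventilated 14 days, alive at Day 28 | 28 − 14 = 14 | 14 |
| Ventilated 20 days, alive at Day 28 | 28 − 20 = 8 | 8 |
| Ventilated Days 1–4, dies on Day 4 on the ventilator | 0 | 0 |
| Ventilated all 28 days, alive | 0 | 0 |

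The first patient (20) outranks every survivor in the table. The second (17) and third (15) outrank the survivors with 14 and 8. If the day of death is not counted, the three become 19, 16 and 14. The first still exceeds 18 and the second still exceeds 14; the third now ties with 14 but still exceeds 8.

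**Step 2: general condition.** A never-ventilated patient who dies on Day d scores d. A survivor with v ventilator days scores 28 − v. The order is reversed when d > 28 − v. With d and v each from 1 to 27, each v gives v − 1 reversals, so the total is 0 + 1 + … + 26 = 351 of 27 × 27 = 729 combinations (48%). This counts combinations; it is not a probability.

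**Step 3: direction for one patient.** After death no day counts. Had the patient lived, each later day would have added 0 or 1. Death therefore never raises a patient's own score. A never-ventilated patient who dies on Day 3 scores 3; the same patient alive and unventilated to Day 28 scores 28.

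**Step 4: effect on the median.** The documents give neither ICU mortality nor the share of deaths that occur off the ventilator, so the following is an assumption-based range. Assume 60% of patients are ventilated for 3 to 21 days, death days are uniform over Days 3 to 28, and 25%, 50% or 100% of deaths have creditable days before them, with the remaining deaths scoring 0. A large simulated population gives:

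| Assumed mortality | Median, written rule | Median, death = 0 | Difference |
|---|---|---|---|
| 20% | 19–20 | 18 | 1–2 |
| 30% | 16–18 | 16 | 0–2 |
| 40% | 13–17 | 12 | 1–5 |
| 50% | 10–15 | 0 | 10–15 |

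The jump at 50% is mechanical. With 41 patients the median is the (41 + 1)/2 = 21st ranked value, so 21 or more zeros make it 0.

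**Step 5: duration of support.** A patient who dies on the ventilator on Day 2 and a patient extubated on Day 2 both contribute two days. Section 7.5.1 contains nothing that separates them, whereas sections 7.5.3 and 7.5.4 remove deaths from length of stay.

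**The case against.** The strongest reply is that section 7.5.5 says what it measures: days alive and off the ventilator. That is a usable quantity, death does reduce it, and nothing in the plan commits the trial to zero-for-death. This stands in part. Naming the measure for what it is and showing deaths beside it would remove the risk of misreading, but would leave the rank reversals in Step 1.

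A reader might go further and infer that ventilator-free days look better because patients died. The documents do not support that. By Step 3, death can only lower a patient's own score or leave it unchanged; the median is higher only relative to a different scoring rule. That reading fits duration of support alone, where death does shorten the reported figure.

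A reader might also infer that section 7.5.1 summarises duration in all patients. It does not say so; it states no restriction. The gap is an unstated rule. The Day 2 death is also an unusual case, because patients expected to survive less than 72 hours are excluded (section 5.1), although expected and actual survival can differ.

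Finally, these endpoints carry no test or success threshold, 60-day, in-hospital and ICU mortality are all reported, and patients ventilated continuously until death score 0 under either rule. No section mentions decisions against intubation, so how often patients die off the ventilator is unknown. All of this limits the importance of the point without removing it.

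**Conclusion.** The point holds as one of mis-ranking and partial credit. Under section 7.5.5 a patient who dies keeps every ventilator-free day before death and can score above a survivor who recovered from ventilation. This follows from the definition by counting and needs no assumption beyond such courses occurring.

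The effect on the cohort median cannot be computed from the documents. The assumed range runs from no difference to 5 days at 20% to 40% mortality, and from 10 to 15 days at 50%. It depends on mortality and on how many deaths follow time off the ventilator.

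For duration of support, the plan lacks a rule that it does apply to length of stay, so death on support can enter as a short duration.

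The cohort to which ventilator-free days apply is contradictory within the document and must be settled in any case. This is a low-cost improvement to secondary descriptive endpoints. It does not touch the primary endpoints, their tests or the success thresholds in section 7.6.

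**What to change.** In section 7.5.5:

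- Score 0 for any patient who dies on or before Day 28; for survivors, count ventilator-free days through Day 28.
- Report the number of Day 28 deaths beside the median and IQR. This is needed because a survivor ventilated for all 28 days also scores 0.
- State how patients discharged alive with unknown Day 28 status are scored, and report how many there are. Section 7.5.2 already foresees discharged patients who cannot be reached.

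In section 7.5.1, report the duration of each support type separately for survivors and non-survivors.

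Reconcile section 7.5.5 (Cohort 1 only) with the endpoint lists in the Protocol Summary and section 4.1 (non-ICU cohort) before the scoring text is finalised.

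The cost is a few sentences of analysis text. Respiratory support is already captured and follow-up runs to Day 60 or death, so no new data item is needed, but vital status at Day 28 may be missing for some discharged patients. The downside is a less favourable median with more zeros, and possibly a median of 0 if about half the cohort dies by Day 28.

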## 7.6 Sample size considerations

The cohort sizes were selected to achieve at least 80% power of rejecting the null hypotheses at a one-sided 2.5% significance level if the true probability of the primary outcome is at its clinically meaningful value. A single stage exact binomial study design was used.

Cohort 1: With 41 subjects the study will have 80% power to reject the null hypothesis of  $\leq 20\%$  probability of a 2-point decrease in SOFA at a one-sided 2.5% significance level, if the underlying probability is 40%. The treatment will be considered successful if 14 or more subjects achieve the primary endpoint.

Cohort 2: With 90 subjects the study will have 80% power to reject the null hypothesis of  $\geq 60\%$  probability of death, intubation or ICU transfer, if the underlying probability is 45%. The treatment will be considered successful if 44 or fewer subjects achieve the primary endpoint.

## 8. Study procedures

### Consenting Process:

Consent is difficult in patients with acute respiratory symptoms who are in isolation. Therefore, an electronic or phone call or video conference consenting process will be used to document informed consent from patients or HCPOA ([refer to section 13.3 for further details](#)). Research staff will make contact info available to patients who have further inquiries about the project. Once a patient consents to participate in the trial, a member of the study team will assign them a unique patient number (UPN). These UPNs will be assigned to subjects sequentially (MCW-COV-001, MCW-COV-002, MCW-COV-003, etc.). Patients are enrolled on the trial once they have consented and are deemed eligible.

### Day -3 to -0:

1. Subject informed consent (obtained before performing study related activities)
2. Screening (must be completed before enrollment)
3. Baseline Evaluation (at screening) (much of the information will be obtained from the medical record)
  - a. Demographics (age, sex ethnicity, race)
  - b. Medical history (timing of exposure to COVID-19 source patient if known, acute and chronic medical conditions, concomitant medications, allergies. Any medical condition arising after consent should be recorded as AE)
  - c. COVID-19 symptom screen (fevers, cough, shortness of breath), onset of symptoms, source of contagion
  - d. Vital signs
  - e. Physical exam

- f. Chest x-ray or chest CT
- g. ABO type and antibody screen documentation or test if not done
- h. COVID-19 testing (RT-PCR or rapid test) from any source
- i. Pregnancy test (serum or urine) for females of childbearing potential within 7 days prior to infusion
- j. Determination of eligibility as per inclusion/exclusion criteria age.
- k. HCPOA or witness information

